7 ASSESSMENT OF SAFETY

7.1 Adverse Events

7.1.1 Definitions of Adverse Events

Any untoward medical occurrence in a patient or clinical investigation subject administered a pharmaceutical product and which does not necessarily have a causal relationship with this treatment. An adverse event (AE) can therefore be any unfavorable and unintended sign (including an abnormal laboratory finding), symptom, or disease temporally associated with the use of an investigational product, whether or not related to the investigational product.

7.1.2 Recording of Adverse Events

All adverse events of any patient during the course of the trial will be reported in the electronic Case Record Form (eCRF), and the investigator will give his or her opinion as to the relationship of the adverse event to trial drug treatment (i.e., whether the event is related or unrelated to trial drug administration). If the adverse event is serious, it should be reported immediately to Sponsor. Other untoward events occurring in the framework of a clinical trial are also to be recorded as AEs (i.e., AEs that occur prior to assignment of trial treatment that are related to a protocol-mandated intervention, including invasive procedures such as biopsies, medication washout, or no treatment run-in). All AEs regardless of seriousness or relationship to tenalisib, spanning from the informed consent drug until 30 calendar days after the last dose of study drug are to be recorded in the electronic Case Record Form (eCRF).

7.1.3 Handling of Adverse Events

All adverse events resulting in discontinuation from the trial should be followed until resolution or stabilization. Patients must be followed for AEs for 30 calendar days after the last dose of study treatment. All new AEs occurring during this period must be reported and followed until resolution unless, in the opinion of the investigator, the adverse event or laboratory abnormality/ies are not likely to improve because of the underlying disease. In this case, the investigators must record his or her reasoning for this decision in the patient's medical record and as a comment on the eCRF. After 30 days of completion of protocol-specific treatment or discontinuation, only AEs, SAEs, or deaths assessed by the investigator as treatment related are to be reported.

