4.3 Discontinuation from Trial Treatment

The patient will be discontinued from the study in case of any adverse event or procedure that poses increased risk to the patient or interferes with the study conduct; examples include but are not limited to the following:

- NCI CTCAE version 5.0 Grade 3/4 non-hematological toxicities related to study drug that necessitate withdrawal in the opinion of investigator.
- Development of an intercurrent illness, condition, or procedural complication, which could interfere with the patient's continued participation.
- Any other situation where in the opinion of the investigator, continued participation in the study would not be in the best interest of the patient.

CONFIDENTIAL Page 29 of 66

Protocol No. RP6530-2101 Version 1.0, Dated June 29, 2021

In addition, patients will be discontinued from the study in the following circumstances.:

- Consent withdrawal by patient (all patients are free to withdraw from participation in this study at any time, for any reasons, specified or unspecified, and without prejudice).
- Non-compliance by study patients.
- Pregnancy
- Confirmed disease progression during therapy.
- Discontinuation of the study by the Sponsor.

Each patient discontinuation should be discussed with Medical Monitor and the reason for discontinuation should be documented. For all discontinued patients, the end of study safety assessment should be completed at the time of discontinuation. In case of discontinuation due to an AE, patient should be followed up for 30 calendar days from dosing or until resolution/stabilization of AE, whichever is earlier. Patients who have drug related CTCAE grade \geq 3 laboratory abnormalities should be followed until the laboratory values have returned to CTCAE grade \leq 2.

Patients who are discontinued from the study at any stage will be considered for safety analysis. Patients who are discontinued from the study for reasons other than safety may be replaced as advised by the Medical Monitor, unless the Medical Monitor deems it unnecessary based on duration of the follow-up completed by the patient.

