6.9 End of Study (EOS) Visit

All patients must be followed up telephonically for adverse events for 30 calendar days after the last dose of study drug. In case of drug related SAE/AE or treatment discontinuation due to adverse event, the patients will be followed till the resolution/stabilization of the AE or 30 days after the last study dose whichever is the earlier.

CONFIDENTIAL Page 37 of 66

| Table 5 : Schedule of Events | | | | | | | | | | |
|---|-----------|----|-----|----|-----|----|---|---|-------------------|-------------------|
| Cycle | Screening | (| C1 | Ó | 22 | С3 | Monthly visits (C4 onward up to 2 year) ¹⁹ | Efficacy Visits (C5, C7, C9 up to 2 year) ²⁰ | EOT ²¹ | EOS ²² |
| Day | D-28 to 0 | D1 | D15 | D1 | D15 | D1 | D1 | D1 | - | - |
| Window period | - | | ±1 | ±1 | ±3 | ±3 | ±3 | ±7 | +7 | +30 |
| Study Days | D-28 to 0 | 1 | 15 | 29 | 43 | 57 | - | - | - | - |
| Informed Consent ¹ | X | - | - | - | - | - | - | - | - | - |
| Demographics ² | X | - | - | - | - | - | - | - | - | - |
| Medical history ³ | X | X | - | - | - | - | - | - | - | - |
| Vitals ⁴ | X | X | X | X | X | X | X | - | X | - |
| Height and weight ⁵ | X | X | X | X | X | X | X | - | X | - |
| Physical examination ⁶ | X | X | X | X | X | X | X | - | X | - |
| ECOG Performance Status | X | X | - | X | - | - | X | - | X | - |
| Complete blood count ⁷ | X | X | X | X | X | X | X | - | X | - |
| Chemistry panel I ⁸ | X | X | X | X | X | X | X | - | X | - |
| Chemistry panel II ⁹ | X | X | - | X | - | X | X | - | X | - |
| HIV, HBV, HCV status | X | - | - | - | - | - | - | - | - | - |
| PT and INR ¹⁰ | X | X | = | X | - | X | - | - | X | = |
| Cytokines/chemokines analysis ¹¹ | X | - | - | - | - | X | - | - | - | - |
| Urinalysis (routine) | X | X | X | X | X | X | X | - | X | - |
| Pregnancy test ¹² | X | X | - | - | - | - | - | - | - | - |
| 12-lead ECGs ¹³ | X | X | - | X | - | X | - | - | X | - |
| Tumour biopsy 14 | X | - | - | - | - | X | - | - | - | - |
| Radiological assessment (CT and/or MRI) 15 | X | - | - | - | - | X | - | X | X | - |
| Bone scan ¹⁶ | X | - | - | - | - | - | - | - | - | - |
| Drug Dispensing ¹⁷ | - | X | - | X | - | X | X | - | - | - |

CONFIDENTIAL Page 38 of 66

Version 1.0, Dated June 29, 2021

| Tenalisib administration ¹⁸ | - | X | X | X | X | X | X | - | - | - |
|--|---|---|---|---|---|---|---|---|---|---|
| Drug compliance | - | X | X | X | X | X | X | - | X | - |
| AE evaluation | X | X | X | X | X | X | X | - | X | X |

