- 19. All visits will be done monthly from Cycle 3 onwards for 24 months (e.g. C4, C5, C6.... C26).
- 20. All visits for efficacy assessments will be done at 8-weekly intervals (± 7 days) for 24 months (e.g.C5, C7.... C26).
- 21. All patients will undergo the end-of-treatment (EOT) assessments within 7 days after last dose of study drug or discontinuation.
- 22. Patients must be followed telephonically for adverse events for 30 calendar days after the last dose of study drug.

CONFIDENTIAL Page 40 of 66

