7.2 Adverse Event/Serious Adverse Event Causality Assessment

Causality is assessing the relationship of the trial treatment to the adverse event. For this study, the causality assessment will be categorized as related and not related.

- **Related:** All toxicities should be considered related to tenalisib unless there is a clear alternative explanation.
- **Not related:** If there is no temporal association, or another etiology has been identified as the cause, or the trial treatment cannot be implicated based upon the current information.

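### Sections 4.3 and 6.9 allow follow-up of an unresolved adverse event to end at day 30; Sections 7.1.3 and 7.3.2 set no such limit for overlapping events, and nothing says which governs

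*Protocol*

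**What the plan says.** Four protocol sections set the length of adverse event follow-up.

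- **Section 4.3**, for discontinuation due to an AE: "patient should be followed up for 30 calendar days from dosing or until resolution/stabilization of AE, whichever is earlier". It adds, for drug-related abnormalities of grade 3 or higher, that "laboratory abnormalities should be followed until the laboratory values have returned to CTCAE grade" 2 or lower. That rule has no time limit.
- **Section 6.9**, for drug-related AEs and SAEs and for treatment discontinuation due to an AE: "the patients will be followed till the resolution/stabilization of the AE or 30 days after the last study dose whichever is the earlier".
- **Section 7.1.3**, for AEs that cause discontinuation: "All adverse events resulting in discontinuation from the trial should be followed until resolution or stabilization". For events arising in the 30 days after the last dose: "All new AEs occurring during this period must be reported and followed until resolution unless, in the opinion of the investigator", the event is unlikely to improve because of the underlying disease, in which case the reasoning must be recorded.
- **Section 7.3.2**: every SAE from consent to 30 days after the last treatment is reported and followed to resolution.

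The last scheduled contact is the 30-day call. Footnote 22 to Table 5 reads: "Patients must be followed telephonically for adverse events for 30 calendar days after the last dose of study drug".

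**The concern.** Sections 4.3 and 6.9 use 30 days as a point at which follow-up of an open event may end. Sections 7.1.3 and 7.3.2 use 30 days only to bound the period in which events are collected; once an event is open, follow-up ends on a clinical criterion. The same event can fall under both kinds of rule, and neither the protocol nor the SAP says which prevails. A site could drop an open event at day 30 and cite 4.3 or 6.9, while a monitor could cite 7.1.3 or 7.3.2 against it.

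At stake are the safety of patients with open toxicities and the completeness of AE outcome data. The events are foreseeable. Table 7 requires tenalisib to be stopped for grade 3 or life-threatening pneumonitis, for SJS, TEN or DRESS, and for life-threatening diarrhea. None of these is a laboratory abnormality, so the laboratory rule in 4.3 does not cover them.

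**Working it through.** The plan gives no figure to reproduce, so the check sets the rules side by side. Count days from the last dose. Let T_s be the day an event is first resolved or stable, and T_r the day it is resolved, so T_s ≤ T_r.

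| Event | Stop under 4.3 / 6.9 | Stop under Section 7 |
|---|---|---|
| Non-serious AE causing discontinuation | min(30, T_s), both sections | T_s (7.1.3) |
| SAE that is drug-related (6.9) or causes discontinuation (4.3 and 6.9) | min(30, T_s) | T_r (7.3.2) |
| Drug-related, non-serious AE with onset in the 30 days after the last dose | min(30, T_s), 6.9 | T_r, unless the underlying-disease exception applies (7.1.3) |

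**Where the rules part.** All patients are followed by telephone to day 30 in any case, so the practical gap opens at day 30.

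- Row 1: if T_s > 30, the gap is T_s − 30 days. If the event is stable by day 30, the rules agree.
- Rows 2 and 3: if T_r > 30, the gap is T_r − 30 days, even when the event has stabilized, because Section 7 asks for resolution.
- Row 3 is tightest for late onset. An event starting on day d gets at most 30 − d days under 6.9; for d = 30 that is 30 − 30 = 0 days.

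**Internal evidence on intent.** min(30, T_s) can never exceed 30. The special rule in 6.9 for drug-related and discontinuing events therefore never asks for more than the 30 days of telephone follow-up that the sentence before it gives every patient. With *later*, the rule would have a purpose. This suggests a drafting slip, but that is inference; the text does not say so.

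**Two smaller mismatches.** Section 4.3 counts its 30 days from dosing, while 6.9 and 7.1.3 count from the last dose. Section 6.9 caps drug-related events without repeating the uncapped grade 3 or higher laboratory rule of 4.3.

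**Test of the simplest repair.** Replacing min by max gives max(30, T_s) ≥ T_s, which closes row 1. For rows 2 and 3, if T_s ≤ 30 < T_r, then max(30, T_s) = 30 and the gap T_r − 30 remains. Changing one word is not enough for SAEs and new AEs; they need a reference to the Section 7 rule.

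**The case against.** The strongest reply is that the four sections can all be met: a site that applies the longest rule breaches none of them, and Section 11.2 requires the investigator to follow the protocol. That stands. A reader might infer that compliance is impossible, and it is not; what the text leaves open is the required minimum. But 4.3 and 6.9 are stated rules that permit stopping, not merely silent on the matter, so the inconsistency remains.

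Safeguards also count:

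- The laboratory rule in 4.3 covers the most frequent related grade 3 or higher events in Section 1.4 (ALT and AST 7.4% each, neutropenia 4.4%).
- Tables 6 and 7 advise event-based monitoring for several related toxicities, among them rash, diarrhea and transaminitis, which are to be monitored until resolved. This is guidance subject to investigator judgement and mainly concerns on-treatment management.
- After 30 days, "only AEs, SAEs, or deaths assessed by the investigator as treatment related are to be reported", and 7.3.2 keeps later related SAEs reportable.
- Section 4.3 has each discontinuation discussed with the Medical Monitor, and Section 6.1 allows unscheduled procedures when clinically necessary.

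These narrow the gap without closing it. Reporting duties and permission for extra visits do not schedule contact for an open non-serious event after the 30-day call.

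Finally, the analytical consequence is small. The AE summaries in SAP Section 8.8.2 count incidence, grade, relatedness and action taken; AE outcome and duration appear only in listings. That also stands.

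**Conclusion.** The inconsistency holds and is minor. A site following 4.3 or 6.9 could stop at day 30 with a discontinuing AE neither resolved nor stable, or with a drug-related SAE or drug-related new AE unresolved. The effect is on safety follow-up and AE outcome data, not on the primary endpoint or the comparison of doses. The documents do not allow the number of patients to be derived. The conclusion rests on reading 30 days in 4.3 and 6.9 as a permitted end of follow-up, which is their plain wording, and on the absence of any precedence clause in either document.

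Three stronger readings are not supported.

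- A reader might infer from Section 7.2 ("All toxicities should be considered related to tenalisib unless there is a clear alternative explanation") that the cap in 6.9 reaches nearly every toxicity. The same section also allows an event to be called not related when there is no temporal association, or when the treatment cannot be implicated on current information.
- A reader might infer that 6.9 alone governs drug-related, non-serious events that began on treatment and did not cause discontinuation. The laboratory rule in 4.3 and the until-resolved monitoring in Table 7 also reach some of these.
- A reader might measure the problem by counting the event types caught by both kinds of rule. Such a count weights every type equally, so it says nothing about frequency, and it changes according to whether AEs that begin during a dose hold and then cause discontinuation are included.

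**What to change.** In Sections 4.3 and 6.9:

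1. Replace *earlier* with *later*, so that follow-up lasts at least 30 days and continues until the event is resolved or stable.
2. Refer SAEs to 7.3.2 and new AEs in the 30-day window to 7.1.3, so that a stable but unresolved event of these kinds is not released.
3. Repeat in 6.9 the rule in 4.3 for drug-related laboratory abnormalities of grade 3 or higher.
4. In 4.3, count the 30 days from the last dose.

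The cost is wording in two sections and slightly longer follow-up for a few patients, since Section 7 already requires most of it. Some of the extra falls on drug-related, non-serious events that began on treatment and did not cause discontinuation, for which neither 7.1.3 nor 7.3.2 requires follow-up to resolution. SAP Section 5.1 reports that the study closed before all patients had progressed, so the change can help only patients still in follow-up, if there are any.

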7.2 Adverse Event/Serious Adverse Event Causality Assessment

Causality is assessing the relationship of the trial treatment to the adverse event. For this study, the causality assessment will be categorized as related and not related.

- **Related:** All toxicities should be considered related to tenalisib unless there is a clear alternative explanation.
- **Not related:** If there is no temporal association, or another etiology has been identified as the cause, or the trial treatment cannot be implicated based upon the current information.

7.3 Serious Adverse Events

7.3.1 Definitions of Serious Adverse Events

The definitions of serious adverse events (SAEs) are given below. The principal investigator is responsible for ensuring that all staff involved in the trial is familiar with the content of this section.

CONFIDENTIAL Page 41 of 66

An SAE or reaction is defined as any untoward medical occurrence that: results in death, is immediately life-threatening, requires at least a 24-hour in-patient hospitalization or prolongation of existing hospitalization, results in persistent or significant disability/incapacity, is a congenital anomaly/birth defect or any important medical event.

Medical and scientific judgment should be exercised in deciding whether expedited reporting is appropriate in other situations, such as important medical events that may not be immediately life-threatening or result in death or hospitalization, but may jeopardize the patient or may require intervention to prevent one of the other outcomes listed in the previous definition. These should also usually be considered serious. Examples of such events are intensive treatment in an emergency room or at home for allergic bronchospasm; blood dyscrasias or convulsions that do not result in hospitalization; or development of drug dependency or drug abuse. *Progression of malignancy (including fatal outcomes)*, if documented by use of appropriate method (for example, as per RECIST version 1.1 criteria), should not be reported as a serious adverse event.

Treatment within or admission to the following facilities is not considered to meet the criteria of "in-patient hospitalization" (although if any other SAE criteria are met, the event must still be treated as an SAE and immediately reported):

- Emergency Department or Emergency Room
- Outpatient or same-day surgery units
- Observation or short stay in unit
- Rehabilitation facility
- Hospice or skilled nursing facility
- Nursing homes, Custodial care or Respite care facility

Hospitalization during the trial for a pre-planned surgical or medical procedure (one which is planned prior to entry in the trial or planned in advance and not related to the study procedure/drug), does not require reporting as a serious adverse event to the Sponsor.

7.3.2 SAE Reporting by Investigators

It is important to distinguish between "serious" and "severe" adverse events, as the terms are not synonymous. Severity is a measure of intensity; however, an AE of severe intensity need not necessarily be considered serious. For example, nausea which persists for several hours may be considered severe nausea but may not be considered an SAE. On the other hand, a stroke which results in only a limited degree of disability may be considered only a mild stroke but would be considered an SAE. Severity and seriousness should be independently assessed when recording AEs on the eCRF and SAEs on the SAE Report Form.

Adverse events classified by the treating investigator as serious require expeditious handling and reporting to sponsor in order to comply with regulatory requirements. Serious adverse events may occur at any time from the signing of the informed consent form through the 30-day follow-up period after the last trial treatment. Sponsor/sponsor representative must be notified of all SAEs, regardless of causality, within 1 day of the first knowledge of the event by the investigator.

To report an SAE, the SAE Report Form should be completed with the necessary information. All SAEs occurring from the signing of consent until 30 calendar days of last trial treatment must

CONFIDENTIAL Page 42 of 66

be reported to the Sponsor as SAEs on the SAE Report and followed until resolution (with autopsy report if applicable).

Deaths and other SAEs occurring > 30 calendar days after last trial treatment that are deemed related to tenalisib must be reported as SAEs on the SAE Report within 1 day of first knowledge of the event by the treating physician or research personnel (with an autopsy report if available). Deaths occurring > 30 calendar days after last trial treatment and not attributed to trial treatment (e.g., disease progression) need not be reported as SAEs, but simply captured on the appropriate eCRF.

The SAE Report Form should be sent to the sponsor/sponsor representative via fax or e-mail within 24 hours of becoming aware of the event. The detailed SAE reporting process will be reviewed with sites during the site initiation visit as well as provided on the SAE report itself. Transmission of the SAE report should be confirmed by the site personnel submitting the report. Follow-up information for SAEs and information on non-serious AEs that become serious should also be reported to Sponsor as soon as it is available; these reports should be submitted using the SAE Report Form.

Investigators must report SAEs and follow-up information to their responsible IRB/IEC according to the policies of the responsible IRB/IEC.

7.3.3 Sponsor's SAE Reporting Requirements

Sponsor/Sponsor representative is responsible for reporting relevant SAEs to the competent authority, other applicable regulatory authorities, and participating investigators, in accordance with ICH guidelines, and/or local regulatory requirements.

Sponsor/sponsor representative is responsible for reporting unexpected fatal or life-threatening events associated with the use of the trial drugs to the regulatory agencies and competent authorities via telephone or fax within 7 calendar days after being notified of the event.

The Sponsor will report all related, unexpected SAEs, including non-death/non-life-threatening related unexpected SAEs associated with the use of the trial medications to the regulatory authority by a written safety report within 15 calendar days of notification. Reporting to the IRB/IEC will be done according to institutional policy.

7.4 Recording of AE and SAE

Investigators should use correct medical terminology/concepts when recording AEs or SAEs on the SAE Report Forms and AE eCRF. Avoid colloquialisms and abbreviations. All AEs, including those that meet SAE reporting criteria, should be recorded on the AE eCRF; AEs that meet the definition of an SAE should additionally be reported following the procedures noted in above sections.

7.4.1 Diagnosis vs. Signs and Symptoms

All AEs should be recorded individually in the patient's own words (verbatim) unless, in the opinion of the Coordinating Investigator or designated physician, the AEs constitute components of a recognized condition, disease, or syndrome. In the latter case, the condition, disease, or

CONFIDENTIAL Page 43 of 66

syndrome should be named rather than each individual sign or symptom. If a constellation of signs and/or symptoms cannot be medically characterized as a single diagnosis or syndrome at the time of reporting, each individual event should be recorded as an AE or SAE as appropriate on the relevant form(s) (SAE Report Form and/or AE eCRF). If a diagnosis is subsequently established, it should be reported as follow-up information. If a diagnosis is determined subsequent to the reporting of the constellation of symptoms, the signs/symptoms should be updated to reflect the diagnosis.

